2.6 Definition of Subgroups

Subgroups used for analyses of different endpoints are defined in the Table 2 below.

Descriptive statistics will be produced for the different subgroups.

Table 2: Subgroup definition

| Subgroup | Definition | Endpoints |
|------------------------------------|--|--|
| Age group (years) | 
 • <65 years • ≥ 65 years | 
 - Participants' demographics information, baseline disease characteristics, and disposition information - Selected Efficacy - Safety (selected laboratory test results and AE tables) |
| CRS score at baseline ¹ | 
 CRS ≤ 3 CRS ≤ 4 CRS=4 CRS=5 | 
 - Participants' demographics information, baseline disease characteristics, and disposition information - Selected Efficacy - Safety (selected laboratory test results and Adverse events results) |
| | | ○ |

| Subgroup | Definition | Endpoints |
|------------------------|--|--|
| Center ² | 
 Highest recruiter center (located over 2 sites) All other centers | Efficacy (primary and key secondary endpoints) |
| Interim Analysis | 
 Included in Interim Analysis Not included in Interim Analysis | Efficacy (primary and key secondary endpoints) |
| Free IL-6 at screening | 
 $\leq 33\%$ percentile > 33 and $\leq 66\%$ percentile $> 66\%$ percentile | Efficacy (primary and key secondary endpoints) |
| CRP at screening | 
 $\leq 33\%$ percentile > 33 and $\leq 66\%$ percentile $> 66\%$ percentile | Efficacy (primary and key secondary endpoints) |

¹ CRS=5 corresponds to “Use of IMV at the time of randomization”. For descriptive statistics, CRS score at baseline with the subgroups as defined will be used. For inferential statistics, the models should include a baseline CRS flag (≤ 3 /> 3) in combination with the stratification factor. Baseline CRS will not be included in the model.

² Highest recruiter center (located over 2 sites: US1006 & US10033)

Additional subgroup analysis may be specified in a separate analysis plan and reported separately from the clinical study report. These may include subgroups according to baseline C-Reactive Protein or baseline Albumin values.

2.6.1 Pooling Algorithm for Analysis Centers

As per the information in Table 2, certain analysis will be performed using the participants in the following 2 subgroups of the study centers.

- US1006 and US10033.
- All other centers

3 DATA REVIEW COMMITTEE, INTERIM ANALYSIS

A Data Monitoring Committee (DMC) was established to monitor unblinded data to ensure the continuing safety and well-being of the participants. Also, an interim analysis (IA) was conducted during the study. Details for these are described in the next sections.

3.1 Data Monitoring Committee

A DMC consisting of internal and external members was established to monitor unblinded data to ensure the continuing safety and well-being of the participants enrolled in this study. The DMC regularly evaluated the cumulative safety data of all participants in the study. As soon as the first 30 participants received study intervention and had at least 7 days of follow-up after study intervention, the DMC performed an interim data review focused on safety. During this data review enrollment was continued, however, it was planned that recruitment would be halted should 60 patients had been enrolled before the outcome of the data review was known. All data available at the time of the interim data review was included. In case recruitment were to be halted, it was planned to resume the enrollment following a positive assessment of results of these interim data by DMC.

The DMC responsibilities, authorities, and procedures are documented in its charter.

3.2 Interim Analyses

A non-binding unblinded interim analysis (IA) for futility was performed by the sponsor on the primary endpoint when approximately 20% of the planned number of participants had reached Day 28 or could have reached Day 28 by the date of data cut-off for the IA. Results have been discussed with the DMC.

The randomization codes and the translation of randomization codes into treatment and control groups were disclosed to those authorized and only for those participants included in the IA. Following this IA, the study was not stopped for futility.

A separate SAP is available for the interim analysis (IA).

4 SUBJECT INFORMATION

4.1 General

Participants' information will be presented using the ITT and Primary analysis sets unless specified otherwise for a specific display. If there is a difference in allocation (>5 participants) between the ITT and the AST sets the disposition information and demographic and baseline disease characteristics will also be provided for the AST.

For continuous data descriptive statistics will be reported (n, mean, SD, median, range, IQR range), for categorical data frequencies and percentages will be displayed.

4.2 Demographics and Baseline Characteristics

The summary tables for demographic characteristics and baseline values will be generated.

Tables summarizing the following demographic characteristics and baseline values for different measurements during the study are planned.

Demographic and baseline parameters:

- Age (years) including categories (<65; \geq 65)
- Sex (Male, Female)
- Race (White, Black or African American, Asian, American Indian or Alaska Native, Native Hawaiian or Other Pacific Islander, Multiple. ('Not Reported' and 'Unknown' for race will be considered as missing)
- Ethnicity (Hispanic or Latino, Not Hispanic or Latino)
- Baseline weight (kg)
- Baseline height (cm)
- BMI at baseline = Weight at baseline (kg) / (Height at baseline (m))² (If available in the raw data, BMI will be recalculated from last weight and height measurement before start of treatment) and categories (<18.5, 18.5-25, 25-30, \geq 30)
- Smoker (No, Yes - Current, Yes - Former)

Baseline disease characteristics:

- Days from Onset of First Symptoms to Randomization
- Level of Hospital Care at Baseline (Hospital inpatient department (ward), Intensive care unit, Step down unit)
- Days from Onset of First Symptoms to First Admission in Hospital (Regardless of Level of Care)
- Days from First Admission in Hospital (Regardless of Level of Care) to screening
- Days from First Admission in ICU to screening
- Days from First Symptoms to IMV and/or ECMO
- Chest Imaging (Normal, Abnormal, Unilateral findings, Bilateral findings)
- Clinical Status at Randomization (Hospitalized - requiring low flow supplemental oxygen, Hospitalized -on non-invasive pressure ventilation or high flow, Hospitalized - on IMV or ECMO)

Use of IMV at baseline (based on eCRF data, if not available on eCRF then on IWRS system)
(Yes, No)

Tables summarizing biomarkers and relevant lab tests at baseline will be generated:

- The biomarkers of CRP, D-Dimer, Serum Ferritin, Pro-Calcitonin and Free IL-6 (all from central labs), will be summarized by mean (SD), median, tertiles, IQR, minimum, and maximum. [Note: Measurements below the lower or above the upper limits of quantification (LLOQ, ULOQ) will be imputed as LLOQ/2 or ULOQ, respectively.]
- Lab tests of White Blood cell count, Lymphocyte count, Platelets, Alanine Aminotransferase (ALT), Aspartate Aminotransferase (AST), and Creatinine (all from local labs) will be summarized as per Division of Microbiology and Infectious Diseases (DMID) grades.
- Lab tests of Lactate Dehydrogenase (LDH), Albumin, Troponin-I, and Troponin-T (all from local labs) will be displayed by n and percentages of participants with values of normal, and high/below normal range.

4.3 Disposition Information

Summary tables for the following information showing number and percentages of participants will be generated.

- Participants ‘screened’, ‘screen failures’, ‘randomized and treated’, ‘randomized and not treated’, ‘not randomized and treated’. The table will include all screened participants (only number of participants will be displayed on the table),
- Participants in different analysis sets (only number of participants will be displayed on the table),
- Participants who are ongoing in study, completed the study, discontinued the study and the reasons for discontinuation.

Participants are randomized by two stratification factors (1) Age categories (< 65, \geq 65 years), and (2) Use of IMV at randomization (Yes, No). It is very unlikely but possible that participants are not correctly randomized in the right stratum and that there are discrepancies between IWRS system and information on eCRF pages. A table showing the discrepancies between IWRS system and information on eCRF pages will be generated for participants in RAND analysis set.

4.4 Extent of Exposure and Treatment Compliance

A listing with extent of exposure data (duration of infusion, interruption, and length of interruption) and drug administration information (total calculated dose, participant’s weight, total volume prepared, volume added to IV container) will be provided for each treated participant.

A listing of participants randomized will be generated to show the actual treatment received and randomized treatment and the date/time of the treatment received.

4.5 Protocol Deviations

For the participants in the ITT and Primary analysis sets, the number and percentage of participants with major protocol deviations (using coded major protocol deviations) and number and percentage of participants with major protocol deviations that are considered as affecting the efficacy evaluations will be tabulated. A listing will be generated for screened participants with any major protocol deviations and the major protocol deviations affecting the efficacy evaluations will be flagged.

4.6 Prior and Concomitant Medications

Information on prior and concomitant medications will be provided for the ITT and Primary analysis sets.

Medications taken until the end of study will be summarized by treatment group and overall, by preferred term as frequency tables for the prior and concomitant medications separately:

1. Prior medication: medication that started before the date of the first dose of study drug, regardless of the stop date of the medication.

2. Concomitant medication: (1) medication received on or after the date of first dose of study drug, and (2) medication that was received before dosing date and continued after dosing of study drug, or medication with missing stop date.

It should be noted that a medication may be classified both as prior and concomitant medication.

The classification of a medication will be based only on the date of start/end of the medication and the date of start of study dose; and time portion of medication and study dose will not be considered. Therefore, if a medication started on the study dose date then it is considered as a concomitant medication.

If a medication record has missing components of its start and/or stop dates (day and/or month and/or year), the following rules will be used to impute the missing date or its component:

1. In case of partial start or stop date, the concomitant therapy records will be allocated to prior/concomitant using the available partial information, without imputations.
2. In case of a completely missing start date, the prior/concomitant therapy will be considered as having started before the trial.
3. In case of a completely missing end date, the prior/concomitant therapy will be considered as ongoing at the end of the trial.

The analysis of prior/concomitant medications will use the coded terms from the WHO drug dictionary as provided in the clinical database.

The number and percentage of participants with prior and concomitant medications will be summarized by ATC levels 1, 2, 3, and by standardized medication names (coded terms).

Medications of interests with COVID-19: The following medication groups of the prior and concomitant medications of interests with COVID-19 will be summarized showing number and percentage of participants by medication groups/coded terms:

- Covid-19 direct antiviral,
- Remdesivir and Glucocorticosteroids,
- Glucocorticosteroids for systemic use,
- Antibacterial for systemic use,
- Antimycotics for systemic use, and
- Antithrombotic agents (excluding antiplatelets)
- Convalescent plasma
- Interleukin Inhibitors
- COVID-19 Vaccine

The above groups and corresponding coded terms will be listed in the DPS.

Duration of medications of interests with COVID-19: The median, range and interquartile range of duration (Days) of treatment with Remdesivir and Glucocorticosteroids during the study will be tabulated.

4.7 Medical history

Medical history for each participant will be collected at screening visit. Summary of medical history will be presented using the ITT and the Primary analysis sets.

General medical history and COVID-19 related medical history are collected on separate pages of the eCRF. COVID-19 related medical history included the following pre-specified symptoms: Fever, Cough, Sour Throat, Rhinorrhea, Wheezing, Chest Pain, Myalgia, Fatigue/Malaise, and Dyspnea. Any other reported COVID-19 related symptoms not pre-specified in the CRF will be presented under 'Other' with subcategories of Gastrointestinal symptoms, loss of taste/smell, headache, and other. General medical history terms are coded using Medical Dictionary for Regulatory Activities (MedDRA).

General medical history will be tabulated by System Organ Classes (SOC-Med) and Preferred Terms (PT) using MedDRA coding, and by splitting them by those 'being currently active' and 'history and not active'. Additionally, a summary table showing only COVID-19 related medical history will be generated.

Relevant comorbidities at screening are defined by ongoing general medical history related to symptoms of Diabetes, Serious Heart Conditions/Coronary Heart Disease, Chronic Obstructive Pulmonary Disease, Chronic Kidney Disease, Cancer, and Obesity (defined as $BMI \geq 30 \text{ kg/m}^2$ based on height (meter) and weight (kg) at screening). A summary table with number and percentages of participants in each of these comorbidities will be generated. The coded terms (PT) corresponding to comorbidities will be listed in the DPS.

4.8 Physical Examinations and Pregnancy Test Results

For all participants, the targeted physical examinations are performed at screening. Any new findings or worsening of conditions are reported as adverse events (AEs).

For female participants in the AST analysis set, the results of the pregnancy tests at screening/baseline and at Day 28/discharge visits will be listed.

4.9 Results by Sub-groups

As mentioned in the section 2.6, subgroup analysis is planned based on subgroups of (1) age (≤ 65 and > 65 years) and (2) CRS score at baseline (≤ 3 , ≤ 4 , 4, 5) to investigate the disposition of participants during the study, demographic information, and baseline disease characteristics.

5 EFFICACY

Descriptive statistics will be used for all efficacy endpoints and will be tabulated by treatment arm and by the subgroups as specified in table 2.

All efficacy analyses will be performed in the Primary and ITT analysis sets as randomized.

5.1 Analysis Specifications

5.1.1 Level of Significance

The primary endpoint will be tested for superiority of Sirukumab in combination with SOC over placebo in combination with SOC at the 2-sided 5% significance level.

The key secondary endpoints and other secondary endpoints will be tested at the 1-sided 5% significance level.

5.1.2 Stratification Factors

The actual values of the stratification factors will be used for all analyses.

5.2 Primary Efficacy Endpoint(s)

5.2.1 Definitions

Six-point ordinal clinical recovery scale

The 6-point ordinal clinical recovery scale (CRS) provides 6 mutually exclusive conditions ordered from best to worst, and the score reflects the participant's worst situation on the day of the assessment:

1. Not hospitalized
2. Hospitalized, not requiring supplemental oxygen
3. Hospitalized, requiring low flow supplemental oxygen
4. Hospitalized, on non-invasive ventilation, nonrebreather mask or high flow oxygen device
5. Hospitalized, on IMV or ECMO
6. Death

The CRS can be derived from baseline up to and including day 28. The CRS will be missing after trial discontinuation if the participant discontinued the trial for other reason than death. Participants who die before day 28 (before or after discharge from hospital) will be considered to continue the trial up to and including day 28.

The CRS categories are defined below. For ease of categorization, the categories are defined from worst to best. A participant will be evaluated in the same ordering of the categories as below. Once a participant fulfils the criteria for a category, the category is assigned to the participant and the evaluation stops.

6. Death
 - o Participant died at any time on the day of assessment or earlier (all-cause mortality).
5. Hospitalized, on IMV or ECMO

- o IMV or ECMO is used at any time on the day of assessment, OR
- o From a Medical Perspective, the participant should have been on IMV on the day of the assessment

4. Hospitalized, on non-invasive ventilation, nonrebreather mask, or high flow oxygen device
 - o The participant is on supplemental oxygen and the worst FiO₂ is $\geq 50\%$.
3. Hospitalized, requiring low flow supplemental oxygen
 - o On supplemental oxygen with worst FiO₂ $< 50\%$ and the participant was not able to sustain a blood oxygen saturation of $> 93\%$ when breathing room air, OR
 - o Not on supplemental oxygen and the minimum of all available SpO₂ values during the day is $\leq 93\%$
2. Hospitalization, not requiring supplemental oxygen
 - o Hospitalized according to the status described below
1. Not hospitalized, including subjects on low level of oxygen
 - o A distinction will be made between subjects discharged and in need of (score 1.2) or not in need of (score 1.1) oxygen supplementation as indicated by the investigator on the discharge questionnaire. This distinction will not be made when calculating improvements on the CRS, for which score 1 will be used in both cases.

Hospitalization status

The hospitalization status considered for the definition of the CSR will be defined according to the rules described below. The hospitalization status will be evaluated in the same ordering of rules. Once a participant fulfils the criteria, the hospitalization status is defined and the evaluation stops.

1. If a participant is discharged to the alternate care settings ‘different hospital’, ‘acute care facility’, ‘subacute care facility’ or ‘hospice/palliative discharge’, the participant will be considered hospitalized until day 28 or trial discontinuation, whichever comes first. The participant will be categorized in the category the participant was in at time of discharge until trial discontinuation.
2. If a participant is discharged ‘against medical advice’, the participant will be considered hospitalized on the day of discharge and on the day after discharge, unless the participant discontinued the trial. The participant will be categorized in the category the participant was in at time of discharge. The CRS will be considered missing from 2 days after discharge onwards.
3. If a participant is hospitalized although ‘ready for discharge’ according to the investigator, the participant will be considered hospitalized up to and including the first day on which the participant was considered ready for discharge. The participant will be considered “Not hospitalized” from the day after until day 28 or trial discontinuation, whichever comes first (unless the status changes back to “not ready for discharge”).
4. If a participant is discharged although ‘not ready for discharge’ according to the investigator, the participant will be considered hospitalized up to and including 1 day

after the day of discharge, unless the participant discontinued the trial. The participant will be categorized in the category the participant was in at time of discharge. The participant will be considered non hospitalized from 2 days after the day of discharge onwards until day 28 or trial discontinuation, whichever comes first.

5. If a participant is discharged from the hospital, the day of discharge will be considered as “hospitalized”. The participant will be categorized in the category the participant was in at time of discharge. After this day, the participant will be considered “Not hospitalized” until day 28 or trial discontinuation, whichever comes first.

Baseline

The 6-point ordinal CRS at the time of randomization request will be used as the baseline. If the baseline assessment of the CRS is missing, the first available assessment within 12 hours after randomization will be used. If the latter is also missing, the last available assessment prior to baseline will be used.

Sustained Clinical Improvement

Clinical Improvement is obtained if the score on the CRS improved with at least 2 categories with respect to the baseline score.

Sustained clinical improvement is defined as a clinical improvement without documented loss of this clinical improvement up to and including day 28 or until trial discontinuation, whichever comes first.

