5.1. Inclusion Criteria

Each potential participant must satisfy all of the following criteria to be enrolled in the study:

1. Male or female ≥ 18 and < 85 years of age.
2. Hospitalized.
3. Criterion modified by Amendment 4
 - 3.1 Has laboratory-confirmed SARS-CoV-2 infection as determined by real time-PCR at any time before randomization.
4. Criterion modified per Amendment 3
 - 4.1 Evidence of infiltrates by chest X-ray, chest CT, lung ultrasound, or chest auscultation (rales, crackles).
5. Criterion modified per Amendment 2
 - 5.1 Criterion modified per Amendment 3
 - 5.2 Criterion modified per Amendment 5
 - 5.3 Critical COVID-19 disease, defined as:

Critical disease: Requires supplemental oxygen delivered by nonrebreather mask or high-flow nasal cannula OR use of non-invasive or invasive ventilation OR requiring treatment in an ICU.

AND,

corresponding to category 4 on the 6-point ordinal recovery scale (see Section 8.1.1), ie,

Requires one of the above modalities to sustain a $\text{SpO}_2 > 93\%$, with an FiO_2 of 50%^a or higher. Note, the use of other devices may fit with category 4 if the FiO_2 is 50%^a or higher.

OR, corresponding to category 5 on the 6-point ordinal recovery scale, ie,

$\text{PaO}_2/\text{FiO}_2$ ratio < 300 mmHg while on invasive mechanical ventilation or veno-venous ECMO for less than 48 hours prior to screening.

Note: as of protocol amendment 5, patients with confirmed severe COVID-19 disease are no longer eligible in the study. Severe COVID-19 is defined as requiring supplemental oxygen administration by nasal cannula, simple face mask, or other similar oxygen delivery device (ie, above pre-COVID baseline oxygen requirement,

^a The conversion between the oxygen flow expressed in L/min to the corresponding FiO_2 value in % is the following:

L/min	1	2	3	4	5	6	7	8	9	10
FiO_2 %	24	28	32	36	40	44	48	52	56	60

if any, by the participant) at a FiO_2 less than 50%^a. This corresponds to category 3 on the 6-point ordinal scale (see Section 8.1.1).

6. Criterion modified per Amendment 1

6.1 Informed consent must be obtained from the participant (or their legally acceptable representative must sign based on local regulations) indicating that he or she understands the purpose of, and procedures required for, the study and is willing to participate in the study.

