ATTACHMENT 3. CRS DERIVATION

The CRS categories should be evaluated from 6 to 1. First check if the subject falls in category 6 (has the subject died?) if not then we evaluate category 5, if not 5 then evaluate category 4 and so on.

The CRS is evaluated at baseline and per day, relative to the start of the study drug intake. The baseline CRS is based on the data obtained at the time of randomization.

Notes:

- The CRS scores will be calculated up to day 28 for subjects who are still in the trial at day 28. Participants who die before they discontinued the trial before day 28 will be considered to continue the trial up to and including day 28.
- If the subject has different types of oxygen supplementation on a single day, the worst type will be considered to derive the score.
- In case the subject withdrew from the study for other reason than death, the CRS will not be calculated from the next day onwards. A record indicating this type of missing scores should be foreseen in the ADAM data sets.
- Intermittent missing values can occur (eg. Due to incomplete supplementary oxygen information). For intermittent missing values, a record should be foreseen in the adam dataset. It should be possible to make the distinction between this type of missing values and the missing values due to trial discontinuation.

Hospitalized and Not Hospitalized

Rules will be applied in the order as described below. The first rule fulfilled by a subject will be considered.

1. If a subject is discharged to the alternate care settings “2. Different hospital”, “3. Acute Care Facility”, “4. Subacute care facility” or “7. Hospice/Palliative Discharge”, the subject will be considered hospitalized until day 28 or until trial discontinuation. The subject will be categorized in the category the subject was in at the moment of discharge.
2. If a subject is discharged ‘against medical advice’, the subject will be considered hospitalized on the day of discharge and on the day after discharge (unless the subject discontinued the trial). The subject will be categorized in the category the subject was in at the moment of discharge. The CRS will be considered missing on subsequent days.

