 - Receiving supplemental oxygen (through a face mask, nasal cannula, high flow nasal canula or other where FiO2 is $< 50\%$) & the patient was not able to sustain a blood oxygen saturation of $> 93\%$ when breathing room air:
 - If assessed for blood oxygen saturation when breathing room air, SpO2 value should be $\leq 93\%$
 - If not assessed for blood oxygen saturation when breathing room air (for any reason), SpO2 value is assumed to be ≤ 93
 - OR
 - Not on supplemental oxygen and the minimum of all measured SpO2 values during the day $\leq 93\%$ (as this will be measured at least 4 times/day)
- **Score 2:**
 - Hospitalized according to hospitalization rules as discussed earlier.
- **Score 1:**
 - Not hospitalized, including subjects on low level of oxygen.

A distinction will be made between subjects discharged and in need of (score 1.2) or not in need of (score 1.1) oxygen supplementation as indicated by the investigator on the discharge questionnaire. This distinction will not be made when calculating improvements on the CRS, for which score 1 will be used in both cases.

Some examples

Case 1: Discharged from hospital on Day 6 (Rule 5)

| Case 1 | Day 3 | Day 4 | Day 5 | Day 6 | Day 7 | Day 8 to Day 28 |
|-------------------------|--------------|--------------|--------------|------------|-------|-----------------|
| Against medical advice? | | | | --/No | | |
| Status (SS*) | hospitalized | hospitalized | hospitalized | Discharged | | |
| Discharged to** | | | | 1/5/.. | | |
| ready (SS*) | --/Not ready | --/Not ready | --/Not ready | --/Ready | | |
| CRS | >1 | >1 | >1 | >1 | 1 | 1 |

Case 2: Alternate care setting (rule 1): hospitalized until Day 28

| Case 2 | Day 3 | Day 4 | Day 5 | Day 6 | Day 7 | Day 8 to Day 28 |
|-------------------------|--------------|--------------|--------------|------------------------|-------|-----------------|
| Against medical advice? | | | | --/No/YES | | |
| Status (SS*) | Hospitalized | hospitalized | hospitalized | Discharged | | |
| Discharged to** | | | | 2/3/.. | | |
| ready (SS*) | --/Not ready | --/Not ready | --/Not ready | --/Ready/ Not ready | | |
| CRS | >1 | >1 | >1 | >1 | >1 | >1 |

Case 3: Against medical advice (rule 2): hospitalized on Day 6 and 7, missing thereafter

| Case 3 | Day 3 | Day 4 | Day 5 | Day 6 | Day 7 | Day 8 to Day 28 |
|-------------------------|--------------|--------------|--------------|------------------------|-------|-----------------|

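### CRS category 2 has no operative oxygen condition, so the scoring ladder conflicts with the Attachment 3 note that incomplete oxygen data give a missing score

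*SAP*

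**What the plan says.** SAP 5.2.1 and Attachment 3 each set out a ladder tested from worst to best, stopping at the first match ("Once a participant fulfils the criteria for a category, the category is assigned to the participant and the evaluation stops").

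- **Category 4** (5.2.1): "The participant is on supplemental oxygen and the worst" FiO2 that day is at least 50%. Device type is not a criterion.
- **Category 3**: either on oxygen with FiO2 below 50% and unable to hold SpO2 above 93% on room air, or off oxygen with a lowest SpO2 of 93% or less. Attachment 3 words the on-oxygen part as "Receiving supplemental oxygen (through a face mask, nasal cannula, high flow nasal canula or other where" FiO2 is below 50%, and takes an unassessed room-air SpO2 to be 93% or less.
- **Category 2**: headed "Hospitalization, not requiring supplemental oxygen" in 5.2.1, but the criterion beneath is only "Hospitalized according to the status described below". In Attachment 3 it is "Hospitalized according to hospitalization rules as discussed earlier".

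The notes at the start of Attachment 3 add: "Intermittent missing values can occur (eg. Due to incomplete supplementary oxygen information", and ask for these to be flagged separately from values missing after discontinuation. Neither ladder has a step that outputs missing, and neither has a default for an absent FiO2.

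**The concern.** A hospitalised participant on high-flow oxygen, with no FiO2 recorded that day, meets neither category 4 nor category 3 in 5.2.1 and drops to category 2. An inpatient day with no oxygen or SpO2 data does the same. From baseline 4, a score of 2 is exactly the two-category improvement of the primary endpoint; from baseline 5 it is a three-category gain. The key secondary endpoint uses the Day 28 score, so one incomplete Day 28 record could produce a success on both.

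Two programmers working from the same SAP could therefore derive different primary endpoints, depending on whether they code the ladder or the note. Setting every such day to missing is not harmless either. Sustained improvement is lost only through a documented loss, so a missing score can hide a return to oxygen.

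**Working it through.** **1. The ladder applied to three records** (hospitalised, alive, not on invasive ventilation or ECMO)

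| Record for the day | 5.2.1 ladder alone | With the Attachment 3 note | What it can truly be |
|---|---|---|---|
| High-flow, worst FiO2 60% | 4 | 4 | 4 |
| High-flow, no FiO2, room-air SpO2 not assessed | 2 | missing | 3 or 4 |
| No oxygen or SpO2 data | 2 | missing | unknown |

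The last column of row 2 follows from the SAP's own default. If FiO2 was at least 50%, the day is a 4. If it was lower, the unassessed room-air SpO2 is taken as 93% or less and the day is a 3. From baseline 4 that is a gain of 0 or 1 category, never 2. From baseline 5 it is a gain of 1 or 2, so the question stays open.

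**2. When a wrong 2 changes the endpoint** (baseline 4, sustained-improvement rule of SAP 5.2.1)

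- 4 throughout except a 2 on Day 12: no event, because the next 4 is a documented loss.
- 4 throughout except a 2 on Day 28: event on Day 28, and a key secondary success.
- 2 as the last score before discontinuation: event that day. SAP 5.3.2 then counts the participant as a key secondary success.
- 2 at transfer to another care setting: held to Day 28 or discontinuation under hospitalisation rule 1, so an event from the transfer day.
- 2 on the day before a true improvement: event one day early (for example Day 12 instead of Day 13).
- A true 2, then high-flow without FiO2 through Day 28: the event stands whether those days score 2 or missing.
- 4 throughout with Day 28 set to missing: no event.

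**3. The plan's own figures reproduce.** Inputs from SAP 1.4: 74:37 allocation; log-normal time to improvement in survivors, medians 28 and 16.8 days, SD 0.9 on the log scale; Day 28 mortality 40% and 20%; two-sided 5%. Simulation with an unstratified log-rank test (3,000 runs, error about 0.7 points) gives power of 81% with continuous time and 82% with daily time, against at least 80% stated. Control improvement by Day 28 is 0.60 × 0.50 = 30%, as stated. Key secondary power at one-sided 5% is 81.4% for 30% v 55% and 88.7% for 40% v 15%.

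**4. Illustrative size.** Alive and not improved at Day 28:

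- control: 0.60 × (1 − 0.50) = 30.0%
- sirukumab: 0.80 × [1 − Φ(ln(28/16.8)/0.9)] = 0.80 × (1 − 0.715) = 22.8%

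| Assumed share of these with a faulty Day 28 record | Added false success, control | Added false success, sirukumab |
|---|---|---|
| 2% | 0.6 points | 0.5 points |
| 5% | 1.5 points | 1.1 points |
| 10% | 3.0 points | 2.3 points |

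With the same share in both arms, simulated primary power (82% without error) is about 80% at a 5% share, 79–80% at 10% and 76–79% at 20%. The ranges cover placing the false events on Day 28 or on a random day.

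As an extreme case, let there be no treatment effect, with errors in the sirukumab arm only and on random days. Rejection in favour of sirukumab then rises from 2.4% to 4.3% at a 10% share and 7.9% at 20%. Nothing in the documents suggests errors confined to one arm.

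**The case against.** The strongest reply is that the plan already says what happens. Attachment 3 holds the detailed derivation, and its note makes incomplete oxygen information a source of missing scores. The scale is described as mutually exclusive, and the heading of category 2 excludes anyone needing oxygen. A reader might infer that the plan has decided to count such participants as improved. It has not: the conflict is between ladder and note, and the note shows the intent. What survives is that no ladder step carries out that intent, and that missing discards the known fact that the day is a 3 or a 4.

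Other parts of the reply also stand:

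- Protocol 8.1.4 calls for FiO2 four times a day, so every value must be absent before the worst value is unknown.
- In Attachment 3 the FiO2 clause may attach only to other devices. A mask or cannula user without FiO2 would then score 3. That differs from 5.2.1 and is itself a reason to align the two.
- The 30% and 22.8% pools are too large for the missing-FiO2 route, because they include ventilated participants, who score 5 without FiO2. Equal error rates also add slightly more to control, narrowing the difference by about 0.4 points at 5% (1.5 − 1.1).

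Two further inferences are tempting and not supported. One is that critical participants would be scored 2 at baseline and leave the Primary analysis set. Baseline scale data must be collected before randomisation, category 4 entry itself requires FiO2 of at least 50%, and 5.2.1 gives fallbacks for a missing baseline. The other is that flows above 10 L/min have no FiO2. The protocol table ("The conversion between the oxygen flow expressed in L/min to the corresponding" FiO2) stops there, but it already gives 52% at 8 L/min and 60% at 10 and rises throughout, so higher flows fall on the category 4 side.

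**Conclusion.** The point holds as an unreconciled inconsistency in the derivation of the primary endpoint. Category 2 lacks an operative oxygen test in both ladders, and the missing outcome described in Attachment 3 has no step that creates it. It matters only when the faulty record falls on Day 28, is the last before discontinuation, is held after transfer, directly precedes a true improvement, or masks a return to oxygen.

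The likely effect is small: at an assumed 5% share, one to two percentage points of false success per arm and about two points of primary power. These sizes rest on the SAP 1.4 model and on an assumed frequency that the documents do not give. It should still be settled before database lock, because it decides how individual primary events are scored.

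**What to change.** In both SAP 5.2.1 and Attachment 3:

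1. Assign category 2 only if the participant is hospitalised and either (a) off oxygen with SpO2 recorded and every value above 93%, or (b) has a documented room-air SpO2 above 93% and, if on oxygen, a worst FiO2 below 50%.
2. If the participant is on supplemental oxygen with no usable FiO2 and no documented room-air SpO2 above 93%, never assign 2. Record the day as '3 or 4'. For a baseline-4 participant, count it as not improved by two categories and as a documented loss. Otherwise set it to missing, as the Attachment 3 note implies. Use the device-based CRS (As observed) score from SAP 5.4.1 for these days as a sensitivity analysis.
3. Set every other day with insufficient oxygen or SpO2 information to missing, as an explicit step of the ladder.

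Keeping the device-based score to a sensitivity analysis preserves the protocol's choice to split categories 3 and 4 by FiO2 and not by device. The cost is a few lines of SAP text and derivation code; the data are already collected. A blinded count of affected days before lock would show whether the issue arises in practice.
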